EDC	Electronic Data Capture System
FAS	Full Analysis Set
GCP	Good Clinical Practice
GMP	Good Manufacturing Practice
GMT	Geometric Mean Titer
GMI	Geometric Mean Increase
IB	Investigator's Brochure
ICF	Informed Consent Form
IEC	Independent Ethics Committee
MERS	Middle East Respiratory Syndrome
NMPA	National Medical Products Administration
PPS	Per-Protocol Set
RNA	Ribonucleic acid

SAE	Serious Adverse Events
SARS	Severe Acute Respiratory Syndrome
SOP	Standard Operating Procedure
SS	Safety Set
SUSAR	Suspected and Unexpected Serious Adverse Reactions
VED	Vaccine Enhanced Disease
WHO	World Health Organization

CONFIDENTIAL

Amendment History

Amendment 1, Protocol v.2.0

The main purpose of this amendment is to address ICH-GCP content requirements and to incorporate changes and clarifications based on feedback received by investigators.

Amendment 2, Protocol v.3.0

The main purpose of this amendment is to incorporate changes and clarifications based on feedback received by investigators and IRB.

Amendment 3, Protocol v.4.0

The main purpose of this amendment is to revise the interim analysis section and refine the case monitoring workflow.

CONFIDENTIAL

Synopsis

Title of study	Multicenter, Randomized, Double Blind, Parallel Placebo Controlled, Phase III Clinical Trial to Evaluate the Efficacy, Safety and Immunogenicity of Inactivated SARS-CoV-2 Vaccines in Healthy Population 18 years old and above
Protocol number	CNBG2020003SQ
Sponsor	China National Biotec Group Company Limited (CNBG) [name]
Phase of development	Phase III
Planned study duration	Up to 1.5 year. It is designed to be completed when last vaccinated subject is followed-up for a calendar year, unless stopped earlier or extended following recommendation of the DSMB.
Subject participation duration	Planned – up to 1 year.
Locations	The trial will be conducted at approximately 10 institutions in Middle East Area (MEA) and could be extended outside MEA.
Study population	Healthy subjects aged 18 years old and above
Planned number of subjects	Total sample size is 45,000 or more, which are randomly allocated into investigational vaccine 1, investigational vaccine 2 and placebo control group.
Study design	Multicenter, Randomized, Double Blind, Placebo Controlled, Parallel

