4.5. Vaccine efficacy

Research Indicators

$$\text{Vaccine efficacy} = \left(1 - \frac{\text{incidence density of vaccine group}}{\text{incidence density of placebo group}}\right) \times 100\%.$$

Incidence density during the follow-up period = (number of confirmed cases during the effective follow-up period/number of observation years of all vaccinated subjects during the effective follow-up period) × 100%. In the calculation of the number of observation years, the termination of follow-up period is considered as follows: for COVID-19 cases in the subjects, once there are confirmed cases that meet the diagnostic criteria of the "Diagnosis and Treatment Protocol for COVID-19" (the latest version), relevant data will be collected to complete follow-up; For non-cases, the follow-up of vaccine efficacy will be continued until the day of withdrawal from the study.

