5.1.4. Criteria for early withdrawal of subjects from trial

Subjects will be withdrawn from the trial in advance when any of the following conditions occur:

1. The subject or the subject's guardian requests to withdraw from the clinical trial;
2. Intolerable adverse events, whether related to test drugs;
3. The health status of the subjects does not allow them to continue to participate in this trial.
4. The subjects were vaccinated with other investigational vaccines during the study period.
5. Reach the endpoint of clinical trials;
6. Any other reason that the investigator believes.

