6.3.2. Code breaking during the study

(1) Unblinding

When the immunogenicity results for 14 days after the whole course of immunization are obtained, adequate confirmed cases of COVID-19 are collected, the database is locked and unblinded after ensuring that the data are correct, and the safety, immunogenicity and protection effect will be evaluated after unblinding.

(2) Emergency Unblinding

If there is an emergency (such as serious adverse events) in the field work, inform the Ethics Committee and carry out emergency unblinding if necessary.

An online electronic system will be used for emergency unblinding. An investigator will be authorized in the research site, usually the person in charge of the site. When an emergency unblinding occurs in the research site, such as SAEs potentially associated with vaccines, quick knowledge of vaccine groupings is needed, in order to carry out emergency treatment. On-site investigators can log in to their personal authorized account number on the system to initiate an emergency unblinding application. The system will send the emergency unblinding application to the sponsor, PI and monitor simultaneously for approval. After all authorized personnel log in to the system and approved, the online system will inform the on-site person the blind codes of the research number. In case of clustered adverse events or interruption of the trial for any reason, the sponsor and the investigator shall jointly approve for unblinding in advance.

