After unblinding, if the subjects in the experimental group suffer from diseases caused by COVID-19 again, and the disease progresses rapidly, indicating the high probability of ADE or VED. Doctors should be advised to take immune intervention measures to prevent inflammatory storms, or to transfer to a superior hospital in time to prevent more serious injuries due to improper treatment.

(5) Persistent monitoring and long-term safety follow-up of COVID-19 antibodies

According to the requirements of the protocol, the subjects are followed up for a long-term safety period of 12 months, during which serious adverse event information, including disease information caused by COVID-19, is collected through telephone follow-up and active report by the subjects.

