9.3. Statistical Methods

(1) General considerations

Quantitative data will be described by mean, median, standard deviation, minimum and maximum. Frequency and percentage will be used to describe qualitative data and ordinal data.

All analysis will be performed by using SAS 9.4 or later version.

(2) Subject disposition and demographics

The number of subjects randomized, discontinued and completed in each group will be summarized. The discontinued subjects will be listed, including the reason for discontinuation. The number of subjects in the analysis sets will be presented as well.

The demographics of all subjects will be summarized by groups.

(3) Efficacy analysis

The number of cases of admission, dropout, elimination, blood collection, dropout reasons, combined medication and combined vaccines in the experimental and placebo groups shall be described. The percentage of dropout and concomitant medication in the experimental and placebo groups shall be compared with χ^2 test or Fishers exact test.

Protection efficacy (FAS, mFAS and PPS analysis):

The person-year incidence rate of COVID-19 after 14 days following two-dose of vaccination will be calculated in Vaccine-1, Vaccine-2 and placebo groups. Vaccine efficacy from person-year incidence rate of Vaccine-1 and Vaccine-2 with the corresponding 95% CIs will be estimated. The differences between Vaccine-1, Vaccine-2 and placebo will be compared by using Poisson regression model. The person-year incidence rate is calculated by (Number of COVID-19 cases / Person years in exposure of all subjects) \times 100%. In the calculation of person years in exposure, the start date is after 14 days following the 2nd dose. The end date is the diagnosed date of COVID-19 case for ones who are confirmed as COVID-19 cases or last follow-up date for others. Vaccine efficacy (VE)= 1-(person-year incidence in vaccine group/ person-year incidence in placebo group).

Vaccine efficacy after 14 days following two-dose vaccination will be evaluated based on mFAS and PPS. The VE from mFAS population is the primary result, and the efficacy from PPS population is a sensitivity analysis result.

Furthermore, the same statistical methods will be employed to estimate the VE after one dose based on FAS population. Kaplan-Meier plot will be used to depict the incidence of COVID-19 from FAS population.

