If some vaccine group could not reach statistical criteria at the first interim analysis, the cases will be continuously monitored until 100 cases between the vaccine group and placebo group, and the second interim analysis will be activated accordingly. If the vaccine's efficacy reaches statistical criterion in the second interim analysis, it could suggest that the corresponding vaccine satisfies the basic regulatory requirement on the efficacy of an inactivated SARS-CoV-2 vaccine.

If some vaccine group could not reach statistical criteria in the two interim analyses, the cases will be continuously monitored until 150 cases, and the final analysis will be conducted, if the

vaccine's efficacy reaches statistical criterion, it could suggest that the corresponding vaccine satisfies the basic regulatory requirement on the efficacy of an inactivated SARS-CoV-2 vaccine, otherwise, the efficacy will be considered as inconclusive.

If vaccine 1 (or vaccine 2) is conditionally approved for marketing authorization based on interim analysis data from a pivotal clinical efficacy trial, then the cases should be continuously monitored post-marketing authorization, until 150 cases are monitored across vaccine 1 (or vaccine 2) study group and placebo group in order to complete the clinical trial.

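### Efficacy person-time has no end date for vaccination outside the randomised allocation, although case counting continues to 150 cases after a trial vaccine may be authorised

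*Protocol*

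**What the plan says.** Section 9.3(3), repeated in the synopsis, starts efficacy person-time after 14 days following the second dose and gives two end points: "The end date is the diagnosed date of COVID-19 case for ones who are confirmed as COVID-19 cases or last follow-up date for others". Section 4.5 words the end for non-cases differently: "the follow-up of vaccine efficacy will be continued until the day of withdrawal from the study". The primary result comes from the mFAS, which section 9.2 defines by two doses and at least one later efficacy follow-up. That definition has no condition on later vaccination or unblinding.

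Section 9.5 and the synopsis provide that, if a vaccine is conditionally authorised on interim data, "the cases should be continuously monitored post-marketing authorization, until 150 cases are monitored across" that vaccine group and placebo. The synopsis says of the trial's length: "It is designed to be completed when last vaccinated subject is followed-up for a calendar year".

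The only withdrawal criterion in section 5.1.4 that names another vaccine reads: "The subjects were vaccinated with other investigational vaccines during the study period". On unblinding, section 6.3.2 says that once the day-14 immunogenicity results are in and "adequate confirmed cases of COVID-19 are collected, the database is locked and unblinded after ensuring that the data are correct", evaluation follows. It does not say how many cases are enough, or for which of the two comparisons. Section 8.2(4) foresees disease in known vaccine recipients after that point: "After unblinding, if the subjects in the experimental group suffer from diseases caused by COVID-19 again".

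**The concern.** Read together, these sections let counting run into a period when a trial vaccine, or another licensed one, can be obtained outside the trial. The end-date rule is explicit, so this is more than a detail left to a statistical analysis plan: a plan that added a censoring date would change what the protocol states. As written, a placebo recipient who receives an authorised vaccine stays in the placebo denominator while at reduced risk. The placebo incidence falls, the rate ratio rises and VE is underestimated.

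Three results are exposed:

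- the 150-case completion analysis;
- the comparison for the other vaccine, if one vaccine is authorised first, because both comparisons share one placebo arm;
- the VEs against severe disease and death, which section 9.3(3) estimates by the same method.

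**Working it through.** **1. The plan's own figures (section 9.4.1).** Inputs: 150 cases per pair, VE 0.60, bound 0.30, allocation 1:1:1, placebo incidence 0.0085 per year, dropout 15%.

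- N = 150 / [(1 + 1 − 0.6) × 0.0085] = 12,605 per group. Total = 12,605 / 0.85 × 3 = 44,488. Both reproduce.
- Given 150 cases and equal person-time, vaccine-arm cases are Binomial(150, p), with p = (1 − VE)/(2 − VE). Under VE 0.30, p = 0.7/1.7 = 0.412. Under VE 0.60, p = 0.4/1.4 = 0.286.
- The stated 90% power reproduces: 90.0% by normal approximation at one-sided 0.025.
- Exact test at the final level of 0.0231 (section 9.5): 49 or fewer vaccine-arm cases reject (p = 0.0200), while 50 do not (p = 0.0298). The boundary is therefore VE = 1 − 49/101 = 51.5%. Power at VE 0.60 is 88.4%, the reference below.

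**2. Length of the exposed period.** With 15,000 × 0.85 = 12,750 per arm and the planned incidence, a pair yields 12,750 × 1.4 × 0.0085 = 151.7 cases a year. Ignoring staggered entry, going from 50 to 150 cases takes 100/151.7 = 0.66 year (about 8 months), and from 100 to 150 about 4 months.

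**3. Crossover spread over all placebo time.** Let f be the share of placebo person-time accrued after an outside vaccine of efficacy v, at constant risk:

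Apparent VE = 1 − (1 − VE) / (1 − v × f)

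I take VE = 0.60 and v = 0.60, the figure in section 9.4.1. The documents give no f, so the values are assumptions.

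| f | Calculation | Apparent VE | Probability of success at 150 cases |
|---|---|---|---|
| 0 | 1 − 0.4/1.00 | 60.0% | 88% |
| 0.1 | 1 − 0.4/0.94 | 57.4% | 80% |
| 0.2 | 1 − 0.4/0.88 | 54.5% | 68% |
| 0.3 | 1 − 0.4/0.82 | 51.2% | 53% |

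**4. Crossover only after an interim.** Vaccination with a trial vaccine following its authorisation cannot precede the interim that supported it. Let the first m cases be clean, and let a share g of placebo time be crossed over afterwards. Late cases fall in the vaccine arm with probability r/(1 + r), where r = 0.4/(1 − 0.6g). For g = 0.3, r = 0.488 and the probability is 0.328. For g = 0.5, r = 0.571 and it is 0.364.

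| Clean cases | g | Expected vaccine : placebo cases | Apparent VE | Probability of success |
|---|---|---|---|---|
| 100 | 0.3 | 44.96 : 105.04 | 57.2% | 79% |
| 100 | 0.5 | 46.75 : 103.25 | 54.7% | 69% |
| 50 | 0.3 | 47.07 : 102.93 | 54.3% | 67% |
| 50 | 0.5 | 50.65 : 99.35 | 49.0% | 42% |

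Success probabilities are for the 150-case test alone and ignore earlier success at an interim.

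**The case against.** No section plans, permits or mentions vaccinating placebo recipients. A reader might infer from sections 9.3(3) and 9.5 that VE will be biased. The documents support only that it would be if crossover occurred. This stands, and the point is worded accordingly.

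Some safeguards exist. Section 5.1.4 also allows withdrawal for any reason that the investigator sees, and section 4.5 ends efficacy follow-up at withdrawal. Section 9.2 lets the PPS exclude subjects for conditions that may affect efficacy, and section 9.3(3) describes concomitant vaccines by group. These reduce the risk without closing the gap: the first is discretionary, the second is discretionary and serves only a sensitivity analysis, and the third is descriptive.

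A reader might also infer that an interim success unblinds the trial and contaminates case finding. The text does not support that. Unblinding in section 6.3.2 follows database lock, and at the interims only the DSMB sees cases by arm. Passive surveillance is supplemented by weekly calls (Table 4: to day 215), and cases need PCR confirmation and blinded adjudication. What remains is that section 6.3.2 ties unblinding to no case count and to neither comparison.

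Finally, a reader might infer that an authorised vaccine could lose its result. Its interim criterion would have been met before any vaccination that followed its authorisation. The success probabilities above can change a decision only for the other vaccine, or where a vaccine licensed from elsewhere is used. For a vaccine authorised on interim data, the harm is an attenuated completion estimate.

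**Conclusion.** The point holds as a conditional risk that the protocol should remove. The stated person-time rule, combined with counting after authorisation, would classify vaccinated placebo recipients as unvaccinated in the primary mFAS analysis. The direction is toward zero.

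The size depends on crossover shares that the documents do not give. At 60% efficacy for both vaccines, 10% to 30% of all placebo time moves VE from 60% to between 57% and 51%. If crossover begins only after an interim, 30% or 50% gives 57% or 55% after 100 clean cases, and 54% or 49% after 50. These figures assume constant incidence and immediate protection from the outside vaccine.

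**What to change.** In section 9.3(3), section 4.5 and the synopsis, state one common rule. For the primary analysis, person-time ends and cases are counted up to the earliest of:

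- diagnosis;
- receipt of any COVID-19 vaccine outside the randomised allocation;
- unblinding of the subject's allocation to the subject or site for reasons other than managing a suspected COVID-19 episode;
- withdrawal;
- last follow-up or data cut-off.

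Count an episode with onset before the censoring date even if it is confirmed later. This provision and the exception for suspected COVID-19 matter because section 6.3.2 allows emergency unblinding for serious adverse events. Censoring at every such unblinding could selectively remove severe cases.

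Record the dates of outside vaccination and of unblinding on the CRF, and keep the uncensored analysis as a sensitivity analysis.

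In section 6.3.2, define enough cases as completion of the final analysis for both vaccine–placebo comparisons, or a DSMB recommendation, because the placebo arm is shared.

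The cost is amendment wording and two date fields. Fewer post-authorisation cases will count toward 150, so completion may take longer. Some censoring may be informative, and the uncensored analysis is there to show how much that matters.

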7.4.7. Laboratory Testing

All laboratory samples (including Antibody and research samples) will be collected after assessments are performed and before a vaccine is administered at visits that correspond with a dosing day.

Samples for laboratory testing will be collected at time points according to Table 4. Schedule of Events and analyzed by a central and/or local laboratory during the study. Detailed instructions for blood sample collection are in the laboratory manual provided to study sites.

Collect the urines of all women at child-bearing age for pregnancy test, the testing results will be used for enrollment screening. Collect the nasopharyngeal swabs of all the volunteers for RT-PCR testing at the same time of the recruitment, the testing results will be used for subsequent analysis.

Pre-immunization blood collection Day 0

After enrollment, about 12.5ml of venous blood will be collected from all subject before the first dose of vaccine, the serum will be separated within 24 hours and divided into minimum of multiple tubes (each tube was not less than 0.5ml), and stored at -20 °C and below for antibody testing.

Blood collection from the subjects (all suspected or confirmed cases)

After the subjects developed typical COVID-19 symptoms, 12.5 ml venous blood will be collected for antibody testing, serum will be separated within 1-3 days and divided into multiple tubes (each tube was not less than 0.5 ml). Serum is stored at -20°C and below (subjects of confirmed cases and suspected cases are tested for antibodies).

Sample collection after immunization

After enrollment, about 12.5ml venous blood of all the subjects will be collected 14 days after the 2nd dose of immunization. Serum is separated within 24 hours and divided into multiple tubes (each

tube is not less than 0.5 ml), and stored at -20°C and below for immunogenicity antibody testing. The serums from all subjects 14 days after the 2nd dose of immunization will be matched to the serums from the monitored cases for testing of the exploratory immunological protective endpoint. Otherwise, blood samples of 900 or more subjects at each site where allocated sample size is greater than 900 are collected 28 days, 3rd month, 6th month, 9th month, 12th month after 2 doses of immunization, serum is separated within 24 hours and divided into multiple tubes (each tube is not less than 0.5 ml), and stored at -20°C and below for immunogenicity antibody testing.

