The same statistical methods as above are used to evaluate VEs against severe cases of COVID-19 and deaths accompanied by COVID-19.

(4) Immunogenicity analysis (FAS and PPS analysis):

Statistical description: The antibody titer should be logarithmically transformed. Minimum value, maximum value, median and quartile spacing, GMT and 95% CI should be shown.

Comparison of antibody levels before immunization: Logarithmic conversion was carried out on antibody titers, and two independent sample T tests (normal and homogeneous variance) or corrected T tests (normal but uneven variance) shall be used to compare the GMT of neutralizing antibodies against COVID-19 before immunization between the experimental and placebo groups with various ages.

Comparison of antibody levels after immunization:

- ✓ calculate the antibody 4-fold increase rate and 95% CI of anti-SARS-CoV-2 antibody in the experimental and placebo groups with various ages after immunization, and make superiority comparison. If the lower limit of 95% CI of antibody 4-fold increase rate is $\geq 10\%$, the superiority hypothesis is valid;
- ✓ calculate 95% CI of GMT ratio of anti-SARS-CoV-2 antibody in the experimental and placebo group after immunization. If the lower limit of 95% CI ratio is ≥ 1.1 , the superiority hypothesis is valid;
- ✓ calculate the GMI and 95% CI of anti-SARS-CoV-2 antibody in the experimental group after immunization.

(5) Safety analysis (SS analysis)

Describe the frequency and number and incidence of adverse reactions/events. If a subject manifest the same adverse reaction/events repeatedly, the description on this adverse reactions/events should indicate the most severity, the closest relationship with vaccination and the earliest starting time. However, in the list of adverse reactions/events, all adverse reactions/events will be listed.

Using χ^2 test or correct χ^2 test or Fishers exact test, the incidence of total adverse reactions, systemic adverse reactions, local adverse reactions and unexpected adverse reactions in the experimental and placebo groups within 30 minutes, 0-7 days and 8-28 days after inoculation of each dose were compared χ^2 test or correct χ^2 test or Fishers exact is used to compare the difference of SAE incidence rate between the experimental and placebo groups within 360 days after the whole inoculation. The rank sum of two independent samples is used to compare the average grade of adverse reactions in the experimental and placebo groups.

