Referring to the relevant data of Phase I and Phase II clinical trials of this product (the current data are all hypotheses and will be revised later according to the results of Phase I and Phase II clinical trials), the standard deviation of antibody titer is set to be about 0.50 (logarithmic scale). The hypothesis can only be considered as valid when the antibody seroconversion rate and GMT both meet superiority. In order to control the probability of overall type I error, the probability of type I error ($= 0.025/2 = 0.0125$ (one-sided) at each superiority comparison; power is 0.90; The Superiority margin = 0.079 (logarithmic scale, i.e. GMT test group/GMT control group ≥ 1.2 after immunization); The difference D between the average antibody titres (logarithmic scale) of the test group and the control group is 0.20. The standard deviation is 0.5; The experimental group and the control group is designed at a ratio of 1: 1. It is calculated about 425 cases for each group, and 850 cases for each group according to the estimation of 50% dropouts.

Table 6. Sample Size Required for Antibody GMT Superiority Test under Different Parameters

Probability level (One-sided)	Standard deviation (logarithmic scale)	Superiority Margin (Logarithmic Scale)	Mean difference (logarithmic scale)	Power $1 - \beta$	Calculate each group Sample size	Estimated sample size after 50% dropouts
0.0125	0.50	0.041 (ratio 1.1)	0.20	0.90	247	500
0.0125	0.50	0.079 (ratio 1.2)	0.20	0.90	425	850

According to the principle of maximizing the sample size, taking into account the factors of dropouts and the distribution of the number of subjects on the multi-center research site.

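### Baseline titres are significance-tested between randomised arms but do not enter the stated GMT-ratio comparison: a possible loss of precision in a secondary endpoint, not a bias

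*Protocol*

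**What the plan says.** Section 9.3(4) of the protocol, repeated in the synopsis, uses two-sample t-tests, with a correction for unequal variance where needed, on log titres to "compare the GMT of neutralizing antibodies against COVID-19 before immunization between the experimental and placebo groups with various ages". For the titres after vaccination the instruction is to "calculate 95% CI of GMT ratio of anti-SARS-CoV-2 antibody in the experimental and placebo group after immunization", and superiority is declared if the lower limit is at least 1.1. No model and no covariate is named. Baseline enters two other measures, the 4-fold increase rate and the GMI.

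Section 9.4.2(2) sizes the GMT comparison. It sets alpha at 0.0125 ("one-sided) at each superiority comparison; power is 0.90"). For the spread, "the standard deviation of antibody titer is set to be about 0.50 (logarithmic scale"). No correlation with baseline and no residual SD is given.

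Baseline data will exist. Under section 7.4.7, "about 12.5ml of venous blood will be collected from all subject before the first dose of vaccine", and Table 4 schedules a neutralizing antibody test on day 0. Section 9.2(2) requires pre-vaccination immunogenicity data for the full analysis set and results before and after immunization for the per-protocol set. The first-dose exclusions in section 5.1.2 cover confirmed acute SARS-CoV-2 cases, a history of SARS or MERS, and recent symptoms. They include no serological criterion.

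**The concern.** Two choices sit badly together.

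First, after randomisation any baseline difference between arms has arisen by chance, so testing it answers no question. The test is to be run by age group and there are two vaccine arms. At a 5% level about one such test in twenty would come out significant with nothing wrong, and the protocol does not say what would follow.

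Second, the baseline titre has a real use that the stated comparison does not make of it. If some enrolees have been infected before, baseline titres vary and predict later titres, most plainly in the placebo arm, where no vaccine response overlays them. Adjusting for baseline removes chance imbalance from the estimate and reduces its variance. What is at stake is the width of the interval around a secondary immunogenicity estimate.

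**Working it through.** **Inputs from section 9.4.2(2):** one-sided alpha 0.0125; power 0.90; SD 0.50 on the log10 scale; true difference 0.20 ("the average antibody titres (logarithmic scale) of the test group and the control group is 0.20"); margin 0.079 ("The Superiority margin = 0.079 (logarithmic scale, i.e. GMT test group/GMT control group" at least 1.2), with 0.041 (ratio 1.1) as the second scenario in Table 6; equal allocation ("The experimental group and the control group is designed at a ratio of 1: 1").

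**Step 1: reproduce the plan's own figures.** For an unadjusted two-sample comparison,

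n per group = 2 × SD² × (z₀.₉₈₇₅ + z₀.₉₀)² / (difference − margin)², where (2.2414 + 1.2816)² = 12.41.

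- Margin 0.079: 2 × 0.25 × 12.41 / 0.121² = 424 (426 with the t distribution). Stated: 425.
- Margin 0.041: 2 × 0.25 × 12.41 / 0.159² = 246 (247 with the t distribution). Stated: 247.
- Dropout: 425 / (1 − 0.5) = 850, as stated.

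Both figures come from the raw SD of 0.50, so the comparison was sized as an unadjusted one.

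**Step 2: effect of adjusting for baseline.** Let rho be the correlation between log10 baseline and log10 post-vaccination titre, taken as common to the arms. The residual SD is 0.50 × √(1 − rho²), the variance falls by rho², and the interval width on the log scale is multiplied by √(1 − rho²). The documents do not give rho, so a range is assumed. The last column is the factor by which each confidence limit differs from the estimated ratio, 10^(1.96 × residual SD × √(2/425)).

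| Assumed rho | Variance reduction | Width reduction | n per group, margin 0.079 | Power at 425 per group | Limit factor |
|---|---|---|---|---|---|
| 0 | 0% | 0% | 424 | 90.1% | 1.167 |
| 0.1 | 1% | 0.5% | 420 | 90.4% | 1.167 |
| 0.2 | 4% | 2% | 407 | 91.3% | 1.164 |
| 0.3 | 9% | 5% | 386 | 92.7% | 1.159 |
| 0.5 | 25% | 13% | 318 | 96.7% | 1.144 |
| 0.7 | 49% | 29% | 217 | 99.7% | 1.117 |

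**Step 3: does it affect the decision?** Section 9.3(4) applies a margin of 1.1 with a 95% interval. At 425 per group, difference 0.20, SD 0.50 and one-sided 0.025, the unadjusted comparison has about 99.6% power. There is little left to gain on the yes/no question.

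**Step 4: dependence on seroprevalence.** Baseline seroprevalence is not given either. As an illustration with assumed log10 titres, put seronegatives at a constant floor of 0.3 and seropositives at mean 1.5 (SD 0.4). Placebo titres then change only by noise (SD 0.15). Seronegative vaccinees reach 1.5 (SD 0.5), and seropositive vaccinees rise by 0.4 (SD 0.4). The adjusted interval width relative to the unadjusted one is:

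| Seropositive at baseline | 0% | 2% | 5% | 10% | 20% |
|---|---|---|---|---|---|
| Relative width | 1.00 | 0.95 | 0.89 | 0.82 | 0.74 |

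The relation of post-vaccination to baseline titre differs between the arms here, yet a single-slope ANCOVA still does no worse than the unadjusted comparison.

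**The case against.** **This belongs in the SAP.** Section 9 leaves the details of methods to a separate SAP, which is not shown. The protocol never uses the word unadjusted, and sizing on a raw SD is conservative and does not rule out an adjusted analysis. That is fair as far as it goes: the SAP may add the covariate, and the protocol does not forbid it. The baseline significance test, however, is prescribed in the protocol itself, next to a ratio with no baseline term and a sample size built on the unadjusted SD. So the point is more than missing detail.

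**The size is unknown and may be nil.** This stands. Neither rho nor seroprevalence is in the documents. If almost everyone is seronegative, baseline titres lie at the assay floor and adjustment gains almost nothing. The non-zero values of rho are scenarios, not expectations.

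**Baseline is already used.** This stands in part. Section 9.4.2 requires superiority on both the 4-fold increase rate and GMT, and the 4-fold rate is relative to baseline. The GMT half is not.

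**Slopes will differ by arm, so the rho² formula is only approximate.** True of the formula. But with 1:1 allocation within each vaccine-placebo pair, ANCOVA is asymptotically no less precise than the unadjusted ratio.

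**Months 3 to 12.** A reader might infer that the gain falls mainly there, or at every time point. The documents do not support that. The synopsis and section 4.4.2 list only GMT at months 3, 6, 9 and 12; they name no between-arm ratio there, and nothing shows that the correlation with baseline lasts that long.

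**Conclusion.** The point holds as a minor one. The protocol tests baseline titres where a test is uninformative, and it states the GMT ratio without the baseline titre although that titre is available throughout the immunogenicity analysis sets. The consequence is a possible loss of precision: about 0%, 5%, 13% or 29% of interval width at an assumed rho of 0, 0.3, 0.5 or 0.7, and close to nil if seropositivity is rare.

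A reader might also infer that the unadjusted ratio is biased or that the comparison is underpowered. Neither follows. Randomisation protects the unadjusted ratio from systematic bias. The stated sample sizes reproduce, and power is about 90% at the planning margin and about 99.6% at the analysis margin. The superiority conclusion is unlikely to change.

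**What to change.** In section 9.3(4) and the matching synopsis text:

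- Replace the baseline t-tests with a descriptive table of baseline GMT by arm, and by age group if wanted, without p-values.
- At the time points where a between-arm GMT ratio is reported, estimate it for each vaccine against placebo by ANCOVA of log10 post-vaccination titre on arm and log10 baseline titre. Back-transform the arm effect and its 95% interval.
- State in advance that baseline serostatus replaces the titre as covariate if most baseline values lie at the assay floor.
- Keep the unadjusted ratio as a supportive analysis.

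This is a free improvement. It changes analysis wording only and needs no further samples, visits or subjects. The sample size can stay as it is, since it is conservative for the adjusted analysis.
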